7.1 Adverse Events

Adverse events were registered at each point of contact with the patient. Additionally, some adverse events were recorded after a participant made contact or if the investigator otherwise was made aware of any adverse event. Both adverse events reported by the patient and those recorded in hospital records, are registered.

Adverse events were recorded according to an event reporting system (Common Terminology Criteria for Adverse Events (CTCAE version 5.0)). The investigator graded each AE accordingly using the levels mild, moderate severe, life threatening or leading to death. For tabulations, only treatment emerging adverse events (TEAEs) will be presented. TEAEs are defined as AEs with a start date on or after date of first randomised treatment. Any AEs prior to treatment will be listed but not tabulated.

The number (%) of subjects with any TEAEs, with 1, 2 or > 3 TEAEs, with treatment related TEAEs, with treatment emerging serious AEs (TESAE) and TEAEs leading to study drug withdrawal will be summarized by treatment group. The number of events and number (%) of subjects with adverse events by system organ class (SOC) and preferred term (PT) will be summarized by treatment group, overall, for severe AEs and for AEs leading to study discontinuation.

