| Adverse events                       |                     | 1-7, DC  | Χ  | Χ   | Χ                                      | X                   | X                      |
| Survival assessment                  |                     | 1-7, DC  | Х  | Х   | Х                                      | Х                   | х                      |

(DC: Discharge)

\*\*Selected number of patients only

i] And every 7th day onwards if still hospitalized.

ii] All ICU patients and patients on the following medical wards are screened: Infectious diseases, internal medicine, pulmonary medicine and acute medicine. See also own section on screening.

iii] Antibiotics and vitamin B3 containing drugs only.

iv] Full physical examination of all major organ systems.

v] Blood pressure, pulse, temperature, respiration rate and 02 saturation.

[vi] See table 3 below for details.

Table 3: Overview of scoring forms and other assessment methods  $^{**}$ 

| CLINICAL TEST/scoring systems                                    | TIMING  |
|--|---|
|  |   |
| EQ5D (filled in by investigator in the presence of the           | 2 weeks prior to admission. On day 1 and on day 90.                     |
| patient).  |   |
|  |   |
| MOCA   | Day 7 and 90 and week 65.   |
| Trail making A   | Day 7 and 90 and week 65.   |
| Trail making B   | Day 7 and 90 and week 65.   |
| Forward and Backward Recall.                                     | Day 7 and 90 and week 65.   |
| NEWS (completed by nursing staff as part of standard treatment). | - Baseline morning and afternoon, day 3 and day 7.                      |
|  |   |
|  |   |
|  |   |
| 4 meter walking test   | At baseline, day 7, day 90 and week 65.                                 |
| Clinical Frailty score (filled in by investigator)               | Pre-baseline, baseline, day 7, day 90 and week 65.                      |
| Grip strength  | At baseline, day 7, at discharge, day 90 and week 65.                   |
|  | (and every occation at hospital).                                       |
| RASS (completed by nursing staff as part of standard             | Day 0, 1, 3, 7 and every 7 th day thereafter for the         |
| treatment of sedated patients).                                  | duration of stay in ICU   |
|  |   |
| Charlson comorbidity index (Filled in by investigator)           | Baseline  |

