#### 6.2.2 During Treatment

Patients will be monitored and assessed routinely as long as they remain in hospital. Possible adverse reactions are likely to occur during this time, and only patients thought to remain in hospital for at least 7 days are included. This allows the study staff to keep a close eye on all included patients. See 5.1 for detailed description of visits during and after hospitalization.

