#### 6.4 Laboratory Tests

Routine blood samples will be taken at all study visits. During hospitalization these samples will be taken as part of normal hospital routines and usually in the morning. The tests to be taken are listed in table 1, but minor changes may be amended at a later point.

It is beneficial for data analysis to obtain blood tests from as early on during the current illness as possible. Collection of such samples will be done in a pragmatic way by contacting the relevant biobanks or laboratories that might store samples from the participant. This may also include asking the laboratory to pre-emptively freeze patient samples instead of destructing them at the standard time.

Biobanking for other analyses will be performed immediately before the first capsule is administered. If not mentioned otherwise samples will be bio banked according to the groups own SOP (Standard Operating Procedure.

 A separate venous or arterial sample will be collected immediately before the first capsule is administered to analyze NAD+ and metabolites. This sample will be drawn by either the ward staff or the study staff depending upon the location of the patient and presence of existing arterial/venous access. Sampling will mainly be venous at the 90 day follow up when most participants will no longer be in-patients. The study staff will always be present to facilitate swift handling of the sample. This sample should be taken not more than 6 hours prior to the first capsule and at the same time of day on day 7 and 90 if at all possible. NAD+ is unstable and the sample must therefore be transported swiftly to the lab for immediate handling.

- 2) Cytokines (serum/plasma)
- 3) EDTA full-blood rapidly frozen for:
  - a) DNA extraction for DNA methylation arrays
  - b) Sequencing
  - c) SNP arrays
  - d) ChIP-seg and other molecular procedures
- 4) EDTA plasma for biochemical analyses and other analyses
- 5) WBCs for RNA seq
- 6) \*Urine
- 7) \*Buccal swab
- 8) \*Saliva
- 9) Frozen WBC for ChIP-seq/ATAC seq

\*Denotes samples that will only be collected from selected patients which probably will be the second and second last randomization batch (of 5+3 or 10+3 patients) and a similar number of healthy controls (matched by age and sex).

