#### 8.5 Recording of Adverse Events

SE and SAE will be recorded on SA/SAE forms and evaluated according to CTCAE criteria. Any unexpected laboratory value or vital sign will also be recorded as an AE. The CTCAE system will be used to identify levels of abnormality that require reporting. Related clinical signs and symptoms must be noted. Abnormal laboratory results/vital signs will be considered additional information if related to a symptom, sign or diagnosis that warrant reporting on it's own.

The following information will be noted in the AE/SAE forms:

- Dose, way of administration and duration of treatment.
- The nature of the event(s) will be described by the investigator in precise standard medical terminology (i.e. not necessarily the exact words used by the patient).
- The duration of the event will be described in terms of event onset date and event ended data.
- The result of the AE/SAE (Death, life threatening, not yet resolved/still treated for SAE/AE, treated and resolved, improved with sequelae, resolved without sequelae).
- The grade (1-5) according to the CTCAE system.
- The Causal relationship of the event to the study medication will be assessed as one of the following (the definitions below are according to WHO):

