7.2 Clinical Laboratory Parameters

Safety clinical laboratory parameters were collected and assessed, but only used to identify adverse events. Clinical laboratory parameters will be summarized by treatment group and time point.

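### AE detection is denser in hospital than after discharge, so SAP 7.1's crude TEAE counts may be biased if NR changes length of stay, the primary outcome

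*SAP*

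**What the plan says.** **Sources of AEs.** SAP 7.1 states: "Adverse events were registered at each point of contact with the patient". It then adds: "Both adverse events reported by the patient and those recorded in hospital records, are registered". Protocol 8.5 widens the definition: "Any unexpected laboratory value or vital sign will also be recorded as an AE". SAP 7.2 gives the role of the laboratory data: "Safety clinical laboratory parameters were collected and assessed, but only used to identify adverse events".

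**When patients are checked.** Protocol 6.1, Table 1, places the day 3, day 7 and weekly laboratory draws under inpatients and the day 90 and later draws under outpatients. The footnote to Table 2 repeats the assessments every seventh "day onwards if still hospitalized". Protocol 6.4 says of the routine samples: "During hospitalization these samples will be taken as part of normal hospital routines and usually in the morning". Protocol 6.2.2 says: "Patients will be monitored and assessed routinely as long as they remain in hospital".

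**Collection window.** Protocol 8.4 runs AE collection from the first capsule to 30 days after the day 90 visit, for every patient. In SAP 7.1 a TEAE has a start rule but no end date.

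**Analysis.** SAP 7.1 tabulates by treatment group "The number (%) of subjects with any TEAEs, with 1, 2 or > 3 TEAEs", together with related, serious and withdrawal-causing events and event numbers by organ class and term. It plans no rate per patient-day and no split between hospital and post-discharge periods. SAP 1.2 lists NR adverse events as a secondary objective. The primary outcome (SAP 5 and 6.1) is length of hospital stay.

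**The concern.** All patients have the same calendar window, but not the same intensity of observation within it. An inpatient has scheduled blood tests, vital signs and examinations, ward staff nearby and a running hospital record. After discharge, the schedule up to day 90 holds one mid-treatment phone call and no laboratory draw. How many days a patient spends under the denser regime is the very quantity that NR is meant to change.

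If NR shortens stay, its arms get fewer opportunities for an abnormal value to be found. The crude AE table may then look somewhat better with no difference in true risk, or a modest real excess may be diluted. If NR lengthens stay, the bias runs the other way. It would be largest when the trial succeeds on its primary outcome, which is when readers will look hardest at the safety table.

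**Working it through.** **Inputs.** Weibull stay with scale 18 and shape 2.2, and a maximal reduction of 33% (SAP 2.3). Check days 3, 7, 14, 21 and so on while in hospital, plus day 90 (Protocol 6.1). Window of 90 + 30 = 120 days (Protocol 8.4). The reduction is applied as a scaling of time, so the NR scale is 18 × 0.67 = 12.06 with the shape unchanged (assumption).

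**1. The plan's own figure.** Quantile = 18 × (-ln(1-p))^(1/2.2). This gives quartiles of 10.2, 15.2 and 20.9 days, against a stated median of 15 and IQR of 10–21. It reproduces. Neither document states an AE figure.

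**2. Expected scheduled checks after baseline.** A check on day t takes place with probability S(t) = exp(-(t/scale)^2.2).

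| Day | Placebo (18) | 33% shorter (12.06) |
|---|---|---|
| 3 | 0.981 | 0.954 |
| 7 | 0.882 | 0.739 |
| 14 | 0.563 | 0.249 |
| 21 | 0.246 | 0.034 |
| 28 | 0.071 | 0.002 |
| 35 and later | 0.015 | 0.000 |
| **Inpatient total** | **2.76** | **1.98** |
| With day 90 | 3.76 | 2.98 |

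The ratio with day 90 is 2.98/3.76 = 0.79 (-21%). For inpatient checks alone it is 1.98/2.76 = 0.72 (-28%). Checks after day 7 fall from 0.89 to 0.28.

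**3. From checks to AE counts.** Mean stay is 18 × Γ(1 + 1/2.2) = 15.9 days on placebo and 10.7 days with the reduction. That is 13.3% and 8.9% of 120 days. Let r be the ratio of the AE detection rate per inpatient day to that per day after discharge, with true risk equal in both arms. For a window of W days:

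count ratio NR/placebo = (r × 10.68 + W - 10.68) / (r × 15.94 + W - 15.94)

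The documents do not give r, so a range is shown.

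| r (assumed) | W = 120 days | W = 455 days (65 weeks) |
|---|---|---|
| 1 | 1.00 | 1.00 |
| 3 | 141.4/151.9 = 0.93 | 0.98 |
| 5 | 162.7/183.8 = 0.89 | 0.96 |
| 10 | 216.1/263.5 = 0.82 | 0.92 |

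If AEs were found only in hospital, the limit would be 0.67.

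**4. Patients with any AE.** With r = 5 and W = 120, a placebo mean of 1 AE gives 62.7% v 58.5%. A placebo mean of 3 gives 94.4% v 92.6%. Event numbers and count categories therefore move more than the percentage with any AE, particularly when AEs are common.

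**The case against.** A reader might infer that a shorter stay by itself lowers the AE count in proportion and makes NR look safer. The documents do not support that.

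- **Other sources.** Patient report is an AE source in the same SAP sentence. Protocol Table 2 seeks AEs at discharge, the mid-treatment call, day 90, about week 65, withdrawal and follow-up. The calendar window in Protocol 8.4 is common to all. A gap until day 90 exists for scheduled laboratory draws, not for AEs in general.
- **Checks are not AEs.** Protocol 8.5 uses CTCAE levels to decide which abnormalities need reporting, and treats abnormal values as additional information when they belong to a reportable diagnosis. The -21% describes opportunities for detection only.
- **Size.** The 33% is a maximum and need not hold at every dose. Taking 0.10 AEs per inpatient day and 0.02 per day afterwards (assumption, r = 5), the means are 3.68 v 3.25. If counts are Poisson, the standard error of that difference with 18 v 20 patients is √(3.68/18 + 3.25/20) = 0.6, larger than the difference of 0.4. The AE tables are descriptive; SAP 2.4 reserves hypothesis tests for the primary outcome.
- **Direction.** It depends on NR changing stay. For SAEs it is unclear: an event that leads to admission after discharge is serious under Protocol 8.1.2, while the same event managed during the first stay may not be. A shorter stay might also truly prevent some hospital-related events.
- **Partial cover.** SAP 7.2 and 7.3 already summarise laboratory values by time point and vital signs by time point during admission.

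All of this stands and limits the point. It does not remove it: equal calendar time is not equal detection, and SAP 7.1 offers nothing that would let a reader judge the difference.

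**Conclusion.** The concern holds as a possible bias of unknown size. It rests on three documented facts: laboratory and vital-sign findings can be AEs, scheduled checks between day 3 and day 90 depend on remaining in hospital, and SAP 7.1 plans only crude counts. Under the planning model at the maximal reduction, scheduled checks including day 90 fall by 21%. AE counts would fall by about 7% to 18% over 120 days for r of 3 to 10, and by about 2% to 8% over 65 weeks. Both ranges assume r and equal true risk; with r = 1 there is no bias. Laboratory- and vital-sign-derived AEs are the most exposed. No direction can be claimed for SAEs.

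Two stronger readings should be resisted. First, one might make AEs from days 1–7 the main comparison, as if observation were equal there. It is not: under the planning model 12% of placebo patients and 26% with the full reduction leave by day 7 (1 - 0.882 and 1 - 0.739). It would also move later harms of a 90-day treatment out of the main table. Second, one might infer that patients with exactly three TEAEs are lost. They remain in the any-TEAE row and the event counts, and the symbol may be a misread of at-least-three.

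**What to change.** Keep the full-window TEAE tables in SAP 7.1 as the main safety tables. Add two supportive tables by arm:

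1. TEAEs split by onset in hospital or after discharge, with patient-days at risk in each period. Add a caution that the split conditions on a post-randomisation outcome, so the patients still in hospital may differ between arms.
2. Laboratory- and vital-sign-derived AEs restricted to the checks most nearly common to all patients, namely day 3 and day 90. Show day 7 alongside the number still in hospital.

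State in the text that detection is denser in hospital and that the arms may differ in inpatient days.

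The cost is two extra tables, each with fewer events than the main one. AE onset dates (Protocol 8.5) and discharge times (Protocol 10.5.1) are already collected.

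Editorial: if the SAP really has more than three as its top category, make the categories exhaustive: 1, 2, and 3 or more.

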#### 3 **OVERALL STUDY DESIGN**

The study is a double blinded randomized three stage superiority study where four different doses of NR will be compared to placebo for its efficacy of shortening hospital stays after acute illness. The study will be carried out in multiple departments of Oslo University Hospital and nearby hospital(s).

Study Period Estimated date of first patient enrolled: April, 2019

Anticipated recruitment period: 2 years

Estimated date of last patient completed: November 2021.

Treatment Duration: 3 months

Follow-up: Patients will be followed up for 1000 days as described below (table 5.1). In

addition, epigenetic clocks will be further evaluated by yearly checking the

National Death Registry until all patients are diseased.

#### STUDY POPULATION 4

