|---------------------------------------|---|---|---|---|---|---|
| Total
Cholesterol                  | X | Х | Х | Х | Х | X |
| BIOBANKING:                           |   |   |   |   |   |   |
| 4x EDTA                               | X | Χ |   | Χ | Χ | Х |
| 1x Serum                              | X | Χ |   | Χ | Χ | Χ |
| 1x Plasma                             | X | X |   | Χ | Χ | X |
| 2x CPT                                | X | Χ |   | Χ | Χ | Χ |
| Urine, faeces, saliva,buccal swabs ** | x | x |   | x | x | х |

\* Prior to administration of intervention drug

Table 2: Timing of inclusion and procedures.

|                                      | Screening
period | Treatment Period At inclusion (1), day 3, 7 [i] And on discharge (DC) | Mid-
treatment
follow-up
phone call | Last week
of
treatment
visit at 90
days+/- 10 | End of
study
visit ca
65 wks. | Withdrawal
visit | Follow
up
period |
|--------------------------------------|---------------------|--|--|---|--|---------------------|------------------------|
| Screen patients [ii]                 | Х                   |  |  |   |  |                     |                        |
| Informed consent                     | Х                   |  |  |   |  |                     |                        |
| Inclusion + exclusion criteria       | Х                   |  |  |   |  |                     |                        |
| Medical history, prior treatment.    | Х                   |  | Х  |   |  |                     |                        |
| Treatment dispensed/returned         |                     | 1  |  | ×   |  | х                   |                        |
| Concomitant medication[iii]          | Х                   | 1-7, DC  | Х  | Х   | Х                                      | Х                   |                        |
| Physical examination [iv]            | Х                   | 1-7  |  | Х   | х                                      | Х                   |                        |
| Vital signs [v]                      | Х                   | 1-7  |  | Χ   | X                                      | Х                   |                        |
| Tests/questionnaires [vi] |                     | 1-7,   |  | Х   | Х                                      | Х                   |                        |

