#### 8.4 Time Period for Reporting AE and SAE

For each patient the standard time period for collecting and recording AE and SAEs will begin at day 1 when the first capsule is administered and will continue until 30 days after the end of study visits at day 90. Patients will be asked about side effects, and specifically flushing, at all points of contact with the investigator.

During the course of the study all AEs and SAEs will be proactively followed up for each patient; events should be followed up to resolution, unless the event is considered by the investigator to be unlikely to resolve due to the underlying disease. Every effort should be made to obtain a resolution for all events, even if the events continue after discontinuation/study completion.

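### The SAP's treatment-emergent definition has no end date, so adverse events starting up to about a year after treatment can enter the adverse event tables and dilute an on-treatment difference

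*SAP*

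**What the plan says.** SAP 7.1 defines the term by its start alone: "TEAEs are defined as AEs with a start date on or after date of first randomised treatment". It adds "For tabulations, only treatment emerging adverse events (TEAEs) will be presented", so this definition decides what enters every adverse event table. Those tables, by treatment group, cover:

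- patients with any event and with given numbers of events
- treatment-related events
- serious events
- events leading to drug withdrawal
- events by system organ class and preferred term, including severe events and events leading to study discontinuation

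The documents give different answers on how long events are collected:

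- Protocol 8.4 starts at the first capsule, and collection "will continue until 30 days after the end of study visits at day 90".
- Protocol 6.1, Table 2, has a row "Adverse events" that is also marked under "End of study visit ca 65 wks" and under the follow-up period.
- SAP 7.1 reports that "Adverse events were registered at each point of contact with the patient", and that "some adverse events were recorded after a participant made contact or if the investigator otherwise was made aware of any adverse event". Neither statement has a time limit.

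Protocol section 3 gives "Treatment Duration: 3 months". SAP 2.6 places the main analysis after the week-65 appointment.

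**The concern.** A treatment-emergent table is meant to show events during exposure and a short period after it. With no end date, events from long after the last capsule are counted on the same footing as events on treatment. If NR had an effect only while taken, the later events would accrue at similar rates in both arms and pull the comparison towards no difference.

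Observation time would also vary. SAP 2.7 lets the week-65 visit fall 180 days either side of target, while SAP 7.1 plans counts and percentages without adjustment for time observed.

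Assessing NR adverse events is a secondary objective in SAP 1.2. With groups of 10, 10, 20 and 18 patients, the tables have little capacity to show a difference even before any dilution.

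**Working it through.** The plan states no adverse event rate, so there is no figure of its own to reproduce. The check has two parts.

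**1. Dates**

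- Protocol 8.4 limit: 90 + 30 = day 120 nominally. With the ±7 days of protocol 6.2.3 it is day 113 to 127. With the ±10 days of protocol Tables 1 and 2 it is day 110 to 130. With the SAP 2.7 window for day 90 (−30/+90) it is day 90 to 210.
- Week 65: 65 × 7 = day 455, which is 455 − 90 = 365 days after day 90 and 455 − 120 = 335 days after the 8.4 limit.
- Edges of the SAP 2.7 window: 455 − 180 = day 275 and 455 + 180 = day 635. The later edge is 635 − 90 = 545 days after day 90.
- Share of the nominal span that lies inside the 8.4 period: 120/455 = 26%.

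Late events can plausibly be in the data. Besides the Table 2 row, protocol 8.5 records unexpected laboratory values and vital signs as adverse events, and protocol Table 1 repeats the laboratory panel at week 65.

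**2. Dilution, with assumed rates**

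Assumptions, none from the documents: 60% of placebo patients have an event by day 120; NR raises the rate by half for 90 days and not afterwards; after day 120 the background rate is a fraction f of the early rate.

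- Early daily rate: r = −ln(0.4)/120 = 0.00764
- Placebo cumulative rate to day 455: H0 = r × (120 + 335f)
- NR cumulative rate: H1 = H0 + 0.5 × r × 90 = H0 + 45r
- Proportion with at least one event: 1 − exp(−H)
- Rate ratio: H1/H0 = 1 + 45/(120 + 335f), in which r cancels

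At day 120, H0 = 120r = 0.916 and H1 = 165r = 1.260. The results are:

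| Cut-off | f | Placebo | NR | Rate ratio |
|---|---|---|---|---|
| Day 120 | – | 60% | 72% | 1 + 45/120 = 1.38 |
| Day 455 | 0.1 | 69% | 78% | 1 + 45/153.5 = 1.29 |
| Day 455 | 0.5 | 89% | 92% | 1 + 45/287.5 = 1.16 |
| Day 455 | 1 | 97% | 98% | 1 + 45/455 = 1.10 |

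The rate ratio does not depend on the assumed 60%, but the percentages do. With 20% placebo risk by day 120 and a constant rate, the figures are 20% v 26% at day 120 and 57% v 61% at day 455. The gap then narrows from 6.4 to 3.4 points without approaching 100%.

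If no events after day 120 were collected, as 8.4 read alone implies, the ratio stays at 1.38.

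**The case against.** The strongest reply is that protocol 8.4 already closes the window. If staff followed it, few or no events after about day 120 exist and the missing end date changes almost nothing. That stands as a condition on the size. It does not settle the matter, because Table 2 and SAP 7.1 both point to collection beyond that date and nothing in the SAP removes such events from the tables.

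A reader might infer that the open definition hides a safety signal, that nearly every patient will have an event by week 65, or that all safety tables are compromised. The documents support none of these:

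- They give no event rates, and the dilution ranges from small to nearly complete according to the late rate. That rate may well be lower than the early one, since patients enter while in hospital under repeated assessment and have few scheduled contacts after day 90.
- Treatment-related events and events leading to drug withdrawal are tied to causality or to time on drug, so late events scarcely touch them. Uncommon preferred terms would not saturate.
- Laboratory values and vital signs (SAP 7.2 and 7.3) and mortality, new infections and re-admissions (SAP sections 5 and 6) are summarised without the treatment-emergent definition.

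It is also fair to say that the adverse event tables are descriptive, since SAP 2.4 limits hypothesis testing to the primary outcome, and that a whole-study table has its own use. That argues for showing the later events separately. It does not justify leaving the period undefined.

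**Conclusion.** The point holds as a minor defect in safety reporting. Three passages disagree on how long adverse events are collected, and the SAP's definition lets events from about a year after treatment, later still at the edge of the visit window, count as treatment-emergent. This can dilute an on-treatment difference in the any-event, event-count, serious and organ-class/preferred-term tables.

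Under the stated assumptions (NR rate raised by half during 90 days, equal background rates otherwise), the rate ratio of 1.38 at day 120 becomes 1.29 to 1.10 at day 455 as the late rate goes from one-tenth of the early rate to equal to it. Strict adherence to 8.4 would leave the effect near nil. The primary analysis, the sample size and the type I error are not affected.

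**What to change.** 1. Reconcile protocol 8.4, the adverse event row of protocol Table 2, and SAP 7.1 on the collection period.
2. Add to the SAP definition an end date matching 8.4: 30 days after the day-90 visit, applied alike in all arms whether or not treatment stopped early. Counting from the last dose is not the same period. It would shorten the window for patients who stop early, so follow-up would depend on discontinuation.
3. State whether the day-90 date is nominal or the actual visit, given the three different windows, and what applies to a patient with no such visit. State also how patients are handled whose capsules run past day 90 because dosing was postponed (protocol 5.3).
4. Tabulate events starting after the end date separately by treatment group.

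The cost is a few sentences and one additional table. Onset dates are already recorded under protocol 8.5. The downside is that late events leave the main treatment-emergent table, though late deaths, infections and re-admissions are still reported as outcomes in their own right.
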